### ***Visit 3 (Day 14; Week 2)***

Participant will be asked to report any adverse event(s) or any changes to medications. The Clinical Global Impression – Severity (CGI-S), Clinical Global Impression – Improvement

(CGI-I), MADRS, as well as the CSSRS scales will be used as part of participant assessment. History of caffeine, alcohol, nicotine, and marijuana use will be recorded. Anthropometrics (including weight and waist circumference), resting heart rate and blood pressure data will be measured as well. THINC-it tool will be administered via tablet to evaluate objective and subjective measures of cognitive function. THINC-it tests will be consistently delivered in the following order: Spotter, Symbol Check, Codebreaker, Trails, and PDQ-5-D to all participants with a member of the research team instructing participants to read the tutorial instructions preceding each of the THINC-it tasks. Participants will complete the pen-and-paper version of the Digit Symbol Substitution Test (DSST) and the Trail Making Test B (TMT-B).

Participants will also complete all secondary self-report assessments using paper-based scales/questionnaires and consist of the following scales: Endicott Workplace Productivity Scale (EWPS), Sheehan Disability Scale (SDS), Wellbeing Index (WHO-5), Snaith-Hamilton Pleasure Scale (SHAPS), Generalized Anxiety Disorder (GAD-7), Perceived Deficits Questionnaire for Depression (PDQ-5-D), 36-Item Short Form Survey Instrument (SF-36), Insomnia Severity Index (ISI), Pittsburgh Sleep Quality Index (PSQI), Epworth Sleepiness Scale (ESS) and THINC-it satisfaction questionnaire. All self reports will be administered by a member. All study procedures will take place in a quiet setting.

Participants will receive vortioxetine 10-20 mg (flexibly dosed) over the next 2 weeks to be taken once daily with the option to increase to vortioxetine 20 mg/day based on clinical discretion (e.g. efficacy and tolerability). This dose was chosen based on extant evidence demonstrating improvements in cognitive function (i.e., executive function, attention/speed of processing, and memory), independent of improvement in depressive symptoms, over an 8-week period [19, 20]. Participants will be asked to store the medication at room temperature (i.e., 15-30 °C).

All participants will be fully informed of safety and tolerability concerns related to the treatment and will be instructed to report any treatment emergent adverse events (TEAEs) of concern to a member of the research team. Moreover, members of the research team will specifically probe

and monitor all participants regarding side-effects at each visit. Participants will be advised to contact a research member's 24hr study line in case of side effects. In the event of an emergency, participants are advised to contact their physician or visit the nearest emergency hospital.

***Visit 4 (Day 28; Week 4)***

A member of the research team will complete the MADRS, CGI-I, CGI-S, IPAQ and CSSRS with the participant as well as ask about any side-effects or changes to their medications. History of caffeine, alcohol, nicotine, and marijuana use will be recorded. Anthropometrics (including weight and waist circumference), resting heart rate and blood pressure data will be measured as well. Participants will receive additional vortioxetine for the following 4 weeks.

***Visit 5 (Day 56; Week 8)***

Participant will be asked to report any adverse event(s) or any changes to medications. Anthropometrics (including weight and waist circumference), resting heart rate and blood pressure will be measured as well. History of caffeine, alcohol, nicotine, and marijuana use will be recorded. The CGI-I scale, CGI-S scale, MADRS as well as the CSSRS will also be completed. Participants will be asked to complete the THINC-it to evaluate objective and subjective measures of cognitive function. Participants will complete the pen-and-paper version of the Digit Symbol Substitution Test (DSST) and the Trail Making Test B (TMT-B).

Participants will also complete all secondary self-report assessments using paper-based scales/questionnaires and consist of the following scales: Endicott Workplace Productivity Scale (EWPS), Sheehan Disability Scale (SDS), Wellbeing Index (WHO-5), Snaith-Hamilton Pleasure Scale (SHAPS), International Physical Activity Questionnaire (IPAQ), Generalized Anxiety

Disorder (GAD-7), Perceived Deficits Questionnaire for Depression (PDQ-5-D), 36-Item Short Form Survey Instrument (SF-36), Insomnia Severity Index (ISI), Pittsburgh Sleep Quality Index (PSQI), Epworth Sleepiness Scale (ESS) and THINC-it satisfaction questionnaire. Clinical and research bloodwork will also be collected. All self reports will be administered by a member. All study procedures will take place in a quiet setting. Participants will be required to return completed medication packets.

### **Effort Expenditure for Reward Task (MDD and HC)**

**Optional:** Participants will be asked if they are interested in completing a 20-minute computer based behavioral task to explore effort-based decision-making, called “Effort Expenditure for Reward Task”. This task has been added to objectively measure reward motivation among patients with MDD and HCs. Participants have to select between an Easy and a Hard task. Both tasks involve pressing the Spacebar for a predetermined amount of time. The Hard task offers more money (variable amounts: \$1.24-\$4.30) but is harder and takes twice as long. Participants make their selection knowingly under different win probabilities (i.e. they might not win money even if they are successful if the win probabilities are low).

Participants will be given the option to complete this task at endpoint (Week 8). This task is only done once. Participants will be awarded the monetary value of the amount they win from doing this task. This is a necessary component of the task, as a tangible incentive is required. 30 MDD and 30 HC participants will completed this task only.

### ***Post Visits – Transition to Standard of Care***

Upon completion of the study, patient will be seen by research team clinician to determine whether medication will be discontinued. If medication discontinuation is required, the patient will receive medication reduction by clinician for a period of one week, followed by a period of 1 week with no medication. Patient will be seen by physician 2 weeks post week 8, to monitor well being, including mood, adverse events and any suicide risks. This is a clinical visit with the psychiatrist and will undergo a full clinical psychiatric assessment to assure patient has a smooth

transition to standard of care with their main responsible physician. Should the patient need to see physician sooner, they are advised to contact the 24/7 study line to schedule an appointment. MDD participants will be followed up by physician but will not undergo ongoing provision of care after the study by the research physician.

### **MDD PATIENT SUMMARY CHART**

Visit	Screening (Visit 1)	Week 0 (Baseline, Visit 2)	Week 2 (Visit 3)	Week 4 (Visit 4)	Week 8 (Endpoint, Visit 5)	Post-Study two weeks clinical visit for drug discontinuation. Additional visits will be scheduled as needed.
Consent	X					
Physician visit		X	X	X	X	X
Bloodwork		X			X	
Demographics	X					
Inclusion/ exclusion	X					
Adverse events	X	X	X	X	X	
Current Medications	X					
Medication Changes		X	X	X	X	
M.I.N.I 5.0	X					
SCID	X					
Psychiatric/Medical History	X					
Anthropometrics	X	X	X	X	X	
Lifestyle Factors	X	X	X	X	X	
Montgomery Åsberg Depression Rating Scale (MADRS) > 20	X	X	X	X	X	
THINC-it Practice		X				
THINC-it Cognitive test		X	X		X	
CSSRS	X	X	X	X	X	
DSST (pen/paper)		X	X		X	
TMT-B (pen/paper)		X	X		X	
NART	X					
CGI-I/CGI-S		X	X	X	X	
International Physical Activity Questionnaire (IPAQ)		X		X	X	
Vortioxetine Treatment		X	X	X		
Dispensing medication		X	X	X		
Effort Expenditure for Rewards Task (EEfRT) – optional					X	

Endicott Workplace Productivity Scale (EWPS)		X	X		X	
Sheehan Disability Scale (SDS)		X	X		X	
Wellbeing Index (WHO-5)		X	X		X	
Snaith-Hamilton Pleasure Scale Questionnaire (SHAPS)		X	X		X	
Generalized Anxiety Disorder (GAD-7)		X	X		X	
Perceived Deficits Questionnaire for Depression (PDQ-5-D)		X	X		X	
36-Item Short Form Survey Instrument (SF-36)		X	X		X	
Insomnia Severity Index (ISI)		X	X		X	
Pittsburgh Sleep Quality Index (PSQI)		X	X		X	
Epworth Sleepiness Scale (ESS)		X	X		X	
THINC-it satisfaction questionnaire		X				

## PROCEDURES FOR HEALTH CONTROL PARTICIPANTS

### *Phone Screen*

A member of the research team will assess participants' eligibility based on inclusion/exclusion criteria. Demographics including date of birth, sex, years of education and race will be recorded. Medical history, psychiatric history and lifestyle factors (i.e. alcohol use, nicotine history, caffeine and marijuana use) will also be taken during the phone screen. Participants will also be asked about any current medications that they are currently taking. The CSSRS will also be used

as part of participant assessment. In addition, participants will be asked to report any experience of adverse event(s) prior to study enrollment. Upon confirmation of study eligibility, the participant will be asked to scheduled for future appointment visits.

***Visit 1 (Day 0: Week 1; Baseline)***

The initial visit entails the provision of detailed study information to participant and obtainment of informed written consent. Participants will also be asked to report any experience of adverse event(s) in addition to lifestyle factors. Anthropometrics (consisting of height, weight and waist circumference), resting heart rate and blood pressure will be measured. The MADRS will be completed by a member of the research team trained in MADRS scoring to ensure the participant does not exhibit depressive symptoms (i.e., MADRS total score  $\leq 6$ ). Healthy control participants will be evaluated by the M.I.N.I 5.0 to confirm no diagnosis of mental disorder (including MDD). Participants will also be asked to complete the NART to estimate premorbid IQ.

Participants will be provided with a tutorial to work through the THINC-it. The THINC-it tool will be then administered to evaluate objective and subjective measures of cognitive function. The THINC-it will be consistently delivered in the following order: Spotter, Symbol Check, Codebreaker, Trails, and PDQ-5-D to all participants with a member of the research team instructing participants to read the tutorial instructions preceding each of the THINC-it tasks. Participants will complete the pen-and-paper version of the Digit Symbol Substitution Test (DSST) and the Trail Making Test B (TMT-B).

Participants will also complete all secondary self-report assessments using paper-based scales/questionnaires and consist of the following scales: Endicott Workplace Productivity Scale (EWPS), Sheehan Disability Scale (SDS), Wellbeing Index (WHO-5), Snaith-Hamilton Pleasure Scale (SHAPS), Generalized Anxiety Disorder (GAD-7), International Physical Activity Questionnaire (IPAQ), Perceived Deficits Questionnaire for Depression (PDQ-5-D), 36-Item Short Form Survey Instrument (SF-36), Insomnia Severity Index (ISI), Pittsburgh Sleep Quality Index (PSQI), Epworth Sleepiness Scale (ESS) and THINC-it satisfaction questionnaire. All self reports will be administered by a member. All study procedures will take place in a quiet setting.

Participants will also be provided with a cell phone number accessible 24 hours a day, seven days a week. The cell phone will be carried on a rotating basis by individual members of the research team.

***Visit 2 (Day 14; Week 2)***

Participants will also be assessed with the MADRS. Lifestyle factors, medication updates and adverse events will be recorded. Anthropometrics will be measured (consisting of height, weight and waist circumference), resting heart rate and blood pressure will be measured. Participants will be asked to complete the THINC-it to evaluate objective and subjective measures of cognitive function, in addition to the DSST and TMT-B pen-and-paper cognitive tests.

Participants will also complete all secondary self-report assessments using paper-based scales/questionnaires and consist of the following scales: Endicott Workplace Productivity Scale (EWPS), Sheehan Disability Scale (SDS), Wellbeing Index (WHO-5), Snaith-Hamilton Pleasure Scale (SHAPS), Generalized Anxiety Disorder (GAD-7), Perceived Deficits Questionnaire for Depression (PDQ-5-D), 36-Item Short Form Survey Instrument (SF-36), Insomnia Severity Index (ISI), Pittsburgh Sleep Quality Index (PSQI), Epworth Sleepiness Scale (ESS) and THINC-it satisfaction questionnaire. All self reports will be administered by a member.

***Visit 3 (Day 14; Week 4)***

Participants will be assessed with the MADRS . Lifestyle factors, medication updates and adverse events will also be recorded. Anthropometrics will be measured (consisting of height, weight and waist circumference), resting heart rate and blood pressure will be measured. The International Physical Activity Questionnaire (IPAQ) will be administered as well.

***Visit 4 (Day 56; Week 8)***

Anthropometrics (including weight and waist circumference), resting heart rate and blood pressure will be measured. Lifestyle factors will be measured. Participants will be assessed using the MADRS and be asked about any adverse events. Participants will be asked to complete the THINC-it to evaluate objective and subjective measures of cognitive function. Participants will complete the pen-and-paper version of the Digit Symbol Substitution Test (DSST) and the Trail Making Test B (TMT-B).

Participants will also complete all secondary self-report assessments using paper-based scales/questionnaires and consist of the following scales: Endicott Workplace Productivity Scale (EWPS), Sheehan Disability Scale (SDS), Wellbeing Index (WHO-5), Snaith-Hamilton Pleasure Scale (SHAPS), Generalized Anxiety Disorder (GAD-7), International Physical Activity Questionnaire (IPAQ), Perceived Deficits Questionnaire for Depression (PDQ-5-D), 36-Item Short Form Survey Instrument (SF-36), Insomnia Severity Index (ISI), Pittsburgh Sleep Quality Index (PSQI), Epworth Sleepiness Scale (ESS) and THINC-it satisfaction questionnaire. All self reports will be administered by a member.

### **HEALTH CONTROL SUMMARY CHART**

Visit	Phone Screening	Visit 1 (Baseline, Week 0)	Visit 2 (Week 2)	Visit 3 (Week 4)	Visit 4 (Week 8)
Consent		X			
Demographics	X				
Inclusion/exclusion	X				
Adverse Events	X	X	X	X	X
M.I.N.I 5.0		X			
Psychiatric/Medical History	X				
Current Medications	X				
Changes in Medications		X	X	X	X
Anthropometrics		X	X	X	X
Montgomery Åsberg Depression Rating Scale (MADRS) 6>		X	X	X	X
NART		X			

Lifestyle Factors	X	X	X	X	X
DSST (Pen/Paper)		X	X		X
TMT-B (Pen/Paper)		X	X		X
THINC-it Practice		X			
THINC-it Cognitive test		X	X		X
Effort Expenditure for Rewards Task (EEfRT) – optional					X
International Physical Activity Questionnaire (IPAQ)		X		X	X
CSSRS	X				
SELF REPORTS					
Endicott Workplace Productivity Scale (EWPS)		X	X		X
Sheehan Disability Scale (SDS)		X	X		X
Wellbeing Index (WHO-5)		X	X		X
Perceived Deficits Questionnaire for Depression (PDQ-5-D)		X	X		X
Snaith-Hamilton Pleasure Scale Questionnaire (SHAPS)		X	X		X
Generalized Anxiety Disorder (GAD-7)		X	X		X
36-Item Short Form Survey Instrument (SF-36)		X	X		X
Insomnia Severity Index (ISI)		X	X		X
Pittsburgh Sleep Quality Index (PSQI)		X	X		X
Epworth Sleepiness Scale (ESS)		X	X		X
THINC-it satisfaction questionnaire		X			

## OBJECTIVES

### *Primary Objective:*

❑ To determine the sensitivity of the THINC-it to alterations in cognitive function/performance following intervention with vortioxetine over 8 weeks in adults aged 18-65 with MDD.

### ***Secondary Objectives:***

- ❑ To determine whether early changes (i.e., Day 14; Week 2) in cognitive function/performance, as measured by the THINC-it, predict symptomatic improvements in mood, defined as a reduction of 50% or more on total mood score (as measured by the MADRS), at endpoint.
- ❑ To determine whether early changes (i.e., Day 14, Week 2) in cognitive function/performance, as measured by the THINC-it, are capable of detecting the effect of vortioxetine treatment on secondary outcome measures of function (e.g., SDS, EWPS, WHO-5) at endpoint.

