## **HYPOTHESIS**

The primary aim of this study is to establish sensitivity to change in cognitive function/performance using THINC-it tool in adults (18-65) with MDD treated with vortioxetine (10-20 mg flexibly dosed for 8 weeks). Secondary aims of the study include, but are not limited to: (1) determining whether early changes (i.e., Day 14; Week 2) in cognitive function/performance predict symptomatic improvements in mood (defined as a reduction of 50% or more on total mood score [as measured by the Montgomery Åsberg Depression Rating Scale [MADRS], at endpoint; and (2) determining whether early changes (i.e., Day 14; Week 2) in cognitive function/performance are capable of detecting the effect of vortioxetine treatment on secondary outcome measures assessing functional outcomes [e.g., Sheehan Disability Scale (SDS), Endicott Work Productivity Scale (EWPS), and the 5-Item World Health Organization Wellbeing Index (WHO-5)] at endpoint.

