## STUDY DESIGN

This is an 8-week, open-label, sensitivity to change study assessing alterations in cognitive function/performance, as measured by the THINC-it, in adults (18-65) with Diagnostic and Statistical Manual, Fifth Edition (DSM-5)-defined MDD treated with vortioxetine (10-20 mg flexibly dosed) (N=100) and (N=50) age, and sex-matched, Healthy Controls.

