***Inclusion Criteria for Healthy Controls:***

1. No current or past history of mental disorder as evidenced by the M.I.N.I. 5.0 for DSM-IV.
2. No first-degree relative with an established diagnosis by a healthcare provider of a mood or psychiatric disorder.
3. No unstable medical disorders.

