Participants will receive vortioxetine 10-20 mg (flexibly dosed) over the course of 8 weeks and to be taken once daily with the option to increase to vortioxetine 20 mg/day following visit 3 of the treatment based on clinical discretion (e.g. efficacy and tolerability). This dose was chosen based on extant evidence demonstrating improvements in cognitive function (i.e., executive function, attention/speed of processing, and memory), independent of improvement in depressive symptoms, over an 8-week period [19, 20]. Participants will be asked to store the medication at room temperature (i.e., 15-30 °C).

All participants will be fully informed of safety and tolerability concerns related to the treatment and will be instructed to report any treatment emergent adverse events (TEAEs) of concern to a member of the research team. Moreover, members of the research team will specifically probe and monitor all participants regarding side-effects at each visit. Participants will also be provided with a cell phone number accessible 24 hours a day, seven days a week. The cell phone will be carried on a rotating basis by individual members of the research team.

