## **STUDY MEDICATION: VORTIOXETINE**

Participants receiving vortioxetine will be provided 10 mg/day on days 1–14 of the treatment period, with the option to increase to vortioxetine 20 mg/day at the end of Week 2 based on investigator judgment. For the remaining 6 weeks, the dose of vortioxetine will be flexible at 10 or 20 mg/day as adjudicated by a research clinician.

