is a reasonable expectation that the performance will not be impacted by disease or medication variables. Hence, it is necessary to conduct these analyses in a group of healthy controls (N=50) as compared to an intervention group (N=100) assessing sensitivity to change during vortioxetine treatment flexibly dosed 10-20 mg/day over an 8-week period.

Evidence to date indicates that average performance on cognitive tasks in patients with MDD fall approximately 0.5-1.0 standard deviations (SD) below healthy control normative data that is age, sex and education matched [17]. In this study, a comparison of performance in the healthy control group versus the treatment group with vortioxetine over an 8-week period, flexibly dosed 10-20 mg/day, will demonstrate both the deficit of magnitude as well as margin of improvement following 8 weeks of vortioxetine treatment in the latter group. Data from both groups will allow a comparison of overall THINC-it performance as well as improvement following vortioxetine treatment (sensitivity and specificity) on each test comprising the THINC-it tool.

Interim analysis will be conducted both at primary and secondary measures.

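### The second secondary objective promises detection of a vortioxetine effect on function, but the design can support only an association during treatment

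*Combined protocol and SAP*

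**What the plan says.** The aim appears twice. Under Secondary Objectives, early THINC-it changes are to be examined for whether they "are capable of detecting the effect of vortioxetine treatment on secondary outcome measures of function". The Hypothesis section uses nearly the same phrase: "capable of detecting the effect of vortioxetine treatment on secondary outcome measures assessing functional outcomes". The functional measures named are SDS, EWPS and WHO-5 at endpoint.

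The neighbouring objectives are worded differently. The first secondary objective speaks of predicting mood response, and the primary objective speaks of change following the intervention. Only the second secondary objective refers to the effect of the drug.

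Study Design describes the study as follows: "This is an 8-week, open-label, sensitivity to change study assessing alterations in cognitive function/performance". Its two groups are MDD patients "treated with vortioxetine (10-20 mg flexibly dosed) (N=100) and (N=50) age, and sex-matched, Healthy Controls". The Visit 2 procedures for MDD participants say: "Participants will receive vortioxetine 10-20 mg (flexibly dosed) over the course of 8 weeks". On dose after Week 2, the Study Medication section says "the dose of vortioxetine will be flexible at 10 or 20 mg/day as adjudicated by a research clinician". The first inclusion criterion for controls is: "No current or past history of mental disorder as evidenced by the M.I.N.I. 5.0 for DSM-IV".

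The Test Sensitivity part of the Statistical Plan assigns the secondary objectives to correlations between the THINC-it, or its components, and the secondary measures. The Statistical Plan restricts analyses to participants with complete 8-week data.

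**The concern.** Detecting the effect of a treatment is a causal claim. It needs some information on how comparable patients would have fared without the treatment, and the plan has none. Functional change over 8 weeks in treated patients combines whatever vortioxetine adds with several other sources:

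- placebo response and expectation in an open-label setting;
- the natural course of the episode;
- regression to the mean, since entry requires MADRS of at least 20 at screening and baseline;
- for patients already on an antidepressant, its taper and co-prescription over about 10-14 days (Transition to Enrollment), which is roughly the window in which early change is measured.

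What is at stake is the conclusion. Read literally, the objective would be answered yes by a positive correlation between early THINC-it change and later function. Such a correlation says that patients who change more on one measure also change more on the other. It does not say that vortioxetine caused either change.

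**Working it through.** **The plan's own figure.** The only sample-size figure, 110 evaluable subjects, rests on an effect size of 0.4 for cognitive deficits. It is not a figure for this objective, so there is nothing to reproduce here.

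**Step 1: look for a contrast that could isolate the drug.**

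| Possible contrast | What the plan provides | Usable for a vortioxetine effect on function? |
|---|---|---|
| Treated v untreated MDD | All MDD participants are treated; no randomised, placebo or untreated MDD group is described | No |
| Dose within MDD | 10 mg/day on days 1-14, then 10 or 20 mg/day by clinician judgment | No: no planned variation up to Week 2, and later dose may follow response and tolerability |
| MDD v healthy controls | Controls have no current or past mental disorder and MADRS of 6 or less at baseline | No: they cannot show the course of untreated depression |
| External control or stated assumption | None given | No |

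**Step 2: write the estimand down.** For a treated patient let X be the Week 2 THINC-it change and Y the Week 8 functional change. Write Y = D + B, where D is what vortioxetine adds and B is what would have happened without it. Only Y is observed. Then

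- mean(Y) = mean(D) + mean(B);
- cov(X, Y) = cov(X, D) + cov(X, B).

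Each line has one observable quantity on the left and two unknowns on the right. More patients make the left side more precise but do not split the right side.

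**Step 3: a numerical illustration.** The inputs are assumptions, not taken from the plan. Let u, e1 and e2 be independent standard normal variables, with X = 0.5u + e1 and Y = d + b + 0.5u + e2. Here d is the drug part, b the non-specific part, and d + b = 0.5. By arithmetic:

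- mean(Y) = 0.5;
- SD(Y) = √(0.25 + 1) = 1.118;
- corr(X, Y) = 0.25 / (0.25 + 1) = 0.20.

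None of these depends on how 0.5 divides between d and b. Simulation with 200,000 patients per scenario agrees:

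| d (drug) | b (non-specific) | Mean Y | SD Y | corr(X, Y) |
|---|---|---|---|---|
| 0.50 | 0 | 0.500 | 1.117 | 0.201 |
| 0.25 | 0.25 | 0.499 | 1.118 | 0.202 |
| 0 | 0.50 | 0.503 | 1.119 | 0.200 |

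The remaining differences are simulation error. Different drug effects that produce the same observable data are enough to show that the planned data do not determine the drug effect. The example does not show that the correlation would be the same under every possible mechanism.

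**Step 4: what can be estimated.** corr(X, Y), or a regression of Y on X, is estimable among completers: about 100 × 0.8 = 80 patients at the plan's 20% attrition. The scales needed are collected in MDD participants at Weeks 0, 2 and 8.

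**Step 5: would adjusting for controls help?** Subtracting the controls' mean THINC-it change c from every patient's X gives corr(X − c, Y) = corr(X, Y). The association is unchanged.

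**The case against.** The strongest reply is that this is an instrument study and the phrase is merely loose. The subject of the objective is early THINC-it change, the open-label design is stated plainly, and the analysis promised is a correlation, which is estimable. No section plans to estimate a drug effect on SDS, EWPS or WHO-5, and no reporting text says a correlation will be presented as one. Vortioxetine is also used as a treatment presumed to work, on the strength of cited evidence.

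Much of this stands. The mismatch is between a stated objective and the analysis assigned to it, and the misreporting risk is inferred from the wording. But the causal phrase appears in two sections, and nothing elsewhere limits attribution. The rationale for vortioxetine concerns cognition, not the functional scales.

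Some stronger readings are tempting and are not supported:

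- *Nothing useful can be learned, or the primary aim fails.* Within-patient change and its association with later function are both estimable, and this point does not undo the primary aim.
- *The drug's share of improvement lies anywhere from none to all.* That range is not a derived bound. If patients would have worsened untreated, or the antidepressant taper affected function, the share could fall outside it.
- *The Statistical Plan repeats the causal claim* where it refers to the deficit "as well as margin of improvement following 8 weeks of vortioxetine treatment in the latter group". That phrase is temporal and concerns THINC-it performance, not function.
- *Control-adjusted THINC-it change would repair the objective.* Step 5 shows that it leaves the correlation as it was.

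**Conclusion.** The objective as worded claims something the design cannot deliver. An effect of vortioxetine on function is not identifiable from these data at any sample size, because no comparable patients without the drug are observed and no substitute assumption is stated. This follows from the design. The 0.50, 1.12 and 0.20 in the illustration depend on assumed inputs and serve only as an example.

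The consequence is limited to the wording and interpretation of one secondary objective. It should be corrected because the objective sets what a positive result will be taken to mean.

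**What to change.** Reword the objective in both the Hypothesis and Secondary Objectives sections, for example: *to determine whether Week 2 THINC-it change predicts Week 8 change in SDS, EWPS and WHO-5 during open-label vortioxetine treatment*. This matches the correlations already planned.

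Add one sentence to the Statistical Plan: *this association describes treated patients and is not attributed to vortioxetine*.

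Control-adjusted THINC-it change should not be part of this correction. It bears only on mean THINC-it change, under the primary aim, and removes practice only if patients and controls gain equally from repetition.

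The cost is a narrower claim for one secondary objective. No new data, visits or participants are needed. Keeping the causal wording would instead require a concurrent MDD comparator, which is a different study.
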